2.2 Study Endpoints

2.2.1 Primary endpoints

Safety:

- 1. Incidence of sustained ventricular tachycardia (1~6 Month Post-operation)
 - o Defined as the proportion of patients experiencing ventricular tachycardia lasting more than 30 seconds
- 2. Incidence of newly formed tumors (12 Month Post-operation)
 - o By comparing chest, abdominal and pelvic CT scan and PET-CT scan

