2.2.2 Secondary endpoints

Efficacy:

- 1. Cardiac MRI Assessment of Left Ventricular Function:
 - o Comparative analysis of baseline versus postoperative measurements at 6, and 12 months, including: Infarcted size; End-diastolic lateral wall thickness; Focal septal thickness; Ejection fraction; End-diastolic volume; End-systolic volume; Stroke volume; Cardiac output; Myocardial density; End-diastolic myocardial mass
- 2. Echocardiographic Evaluation of Left Ventricular Function:
 - o Comparative analysis of baseline versus postoperative measurements at 6, and 12 months, including: End-diastolic septal thickness; Left ventricular end-diastolic

diameter; Left ventricular end-systolic diameter; Left ventricular posterior wall thickness at end-diastole; Left atrial diameter; Left ventricular ejection fraction; Mitral inflow velocity profile (E/A ratio)

- 3. Myocardial Perfusion Imaging (PET/ECT):
 - o Comparative analysis of left ventricular perfusion at preoperative, 6-month, and 12-month postoperatively
- 4. Six-Minute Walk Test (baseline, 6 and 12 months)
- 5. NYHA Functional Classification (baseline, 6 and 12 months)
- 6. Minnesota Living with Heart Failure Questionnaire (MLHFQ) (baseline, 6 and 12 months)
- 7. Incidence of Major Adverse Cardiac Events (MACE) including: Mortality; Non-fatal myocardial infarction; Heart failure rehospitalization

Safety:

- 1. Incidence of Perioperative Serious Adverse Events (SAE) Incidence: Mortality; Nonfatal myocardial infarction; stroke; cardiac perforation; cardiac temponade, etc.
- 2. Alloimmune Response Monitoring (PRA, DSA): (baseline, 1, 6 and 12 months)
- 3. Perioperative Electrocardiographic Monitoring (Within 1 month postoperatively)
- 4. Laboratory Tests, including Complete blood count, Comprehensive metabolic panel; NT-proBNP;Troponin; Myocardial enzyme profile; Procalcitonin; Immunological panel (C3, C4, IgA, IgG, IgM); Coagulation profile, etc.

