6.3 Sample Size Determination

This is an exploratory study. The total sample size is 20, with 10 allocated to the cell therapy group and 10 to the control group

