6.5 Statistical Analyses

6.5.1 Primary endpoint analysis

The primary endpoints, including incidence of sustained ventricular tachycardia (1~6 Month Post-operation) and newly formed tumors (12 Month Post-operation) will be analyzed using descriptive statistics (number of observations, mean, median, standard deviation, minimum, and maximum) for continuous variables and using frequencies and percentages for categorical and ordinal variables. A final analysis will be conducted when all subjects have completed the study participation.

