6.5.3 Safety Analyses

Adverse events will be described using the preferred terms from the MedDRA terminology. All adverse events will be graded for severity according to the Common Terminology Criteria for Adverse Events (CTCAE), version 5.0. For Major Adverse Cardiac Events (MACE), including arrhythmias, and for other adverse events and adverse drug reactions distinct from arrhythmias, the number of events and the number of subjects experiencing these events will be determined. Adverse events assessed as Serious Adverse Events (SAEs) will be identified, and the number of such SAEs and the number of subjects experiencing SAEs will be determined. For significant events related to Coronary Artery Bypass Graft (CABG), the number of events and the number of subjects experiencing these events will be determined. Adverse events occurring during or within a specified period following the first administration of the investigational medicinal product will be summarized by CTCAE grade.

Clinical laboratory parameters, vital signs, and physical examination findings will be summarized according to study visit. The analysis will describe the observed values at each visit during the trial as well as the changes relative to baseline values.

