8.4 Post-Transplant Ventricular Arrhythmias Risks and Control

Fatal malignant ventricular arrhythmias constitute a potentially severe risk associated with myocardial cell therapy. Ventricular arrhythmias, particularly polymorphic ventricular tachycardia and ventricular fibrillation, represent significant in-hospital causes of early mortality in myocardial infarction (MI) patients. The resulting tissue architecture, comprising necrotic scar, border zones, and viable myocardium, creates regions of heterogeneous electrophysiology, particularly within the peri-infarct zone, fostering anisotropic conduction and reentrant circuits. Cell therapy targeting the infarcted myocardium inherently modifies this arrhythmogenic substrate. Theoretically, such interventions carry dual potential: therapeutic augmentation of the substrate may reduce arrhythmia susceptibility, while proarrhythmic exacerbation remains a concurrent possibility. Whether cell therapy exerts proarrhythmic effects depends critically upon multiple factors: (1) the specific cell type employed; (2) the degree of electrophysiological integration and coupling between transplanted cells and native myocardium; and (3) intrinsic electrophysiological properties of the transplanted cells themselves. Transplanted cells may introduce novel proarrhythmic substrates by establishing reentrant pathways within scar tissue or inducing arrhythmias via mechanisms of ectopic automaticity or triggered activity.

Animal experimental evidence regarding the proarrhythmic effects of cell-based therapies remains limited and conflicting. Some studies indicate that transplanted cells, which originally lack connexin 43 expression, can acquire this critical gap junction protein postengraftment; connexin 43 is essential for facilitating coordinated electrical conduction within myocardial tissue. However, persistent concerns exist based on studies suggesting that cardiomyocytes derived from embryonic stem cells (ESCs) may harbor intrinsic proarrhythmic risks. Notably, research by Shiba et al. demonstrated that treatment of heart failure in nonhuman primates using induced pluripotent stem cell (iPSC)-derived cardiomyocytes did not result in fatal arrhythmias [18].

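### The primary arrhythmia endpoint counts only VT lasting more than 30 seconds, so ventricular fibrillation, VT terminated earlier, and arrest or sudden death without recorded VT of that length fall outside the primary safety result

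*Protocol*

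**What the plan says.** The protocol synopsis and Section 2.2.1 list the same first primary endpoint, "Incidence of sustained ventricular tachycardia (1~6 Month Post-operation"), with one line of definition: "Defined as the proportion of patients experiencing ventricular tachycardia lasting more than 30 seconds". Section 6.5.1 repeats the endpoint's name and summarises it "using frequencies and percentages for categorical and ordinal variables". It adds no event criterion and no rule for patients who die in the window.

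Section 8.4 opens with the risk that the endpoint is there to watch: "Fatal malignant ventricular arrhythmias constitute a potentially severe risk associated with myocardial cell therapy". It continues: "Ventricular arrhythmias, particularly polymorphic ventricular tachycardia and ventricular fibrillation, represent significant in-hospital causes of early mortality". That second sentence goes on to limit itself to patients with myocardial infarction, so it is background and not a statement about the cell product. Exclusion criterion 6 in Section 3.2 treats a history of sustained VT and a history of sudden cardiac death together as one bar to entry.

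The other places where a serious arrhythmia could be counted are:
- **Section 2.2.2:** "Incidence of Major Adverse Cardiac Events (MACE) including: Mortality; Non-fatal myocardial infarction; Heart failure rehospitalization". Mortality here is all-cause. The separate serious adverse event (SAE) endpoint is perioperative.
- **Section 6.5.3:** "For Major Adverse Cardiac Events (MACE), including arrhythmias, and for other adverse events and adverse drug reactions distinct from arrhythmias", with events and subjects both counted, and the same for SAEs.

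On size, Section 6.3 states: "The total sample size is 20, with 10 allocated to the cell therapy group and 10 to the control group".

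**The concern.** The primary safety endpoint should register the harm that the protocol itself calls potentially severe. As worded, it registers one form of that harm, identified by its duration. VF is not VT, so VF alone cannot meet the definition. VT that is terminated quickly because the patient is compromised cannot meet it either, since the intervention stops the clock. An arrest or sudden death qualifies only if VT of more than 30 seconds was recorded first.

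The primary analysis is descriptive, so the reported proportion is itself the primary result. A reader who sees 0/10 on the primary arrhythmia endpoint will take it as the trial's summary of arrhythmic safety, although a malignant arrhythmia may be listed in a later safety table. The event definition is fixed in the protocol, and an analysis plan that added VF would contradict it.

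**Working it through.** **Step 1. Classify each type of event in months 1 to 6 under the wording as it stands.**

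| Event | Primary endpoint (2.2.1) | Where else it appears |
|---|---|---|
| VT over 30 s, any morphology | Counted | 6.5.3 |
| VT over 30 s recorded, then VF or death | Counted | 6.5.3; death in MACE (2.2.2) |
| VT terminated before 30 s | Not counted | 6.5.3 |
| VF with no qualifying VT before it | Not counted | 6.5.3 |
| Resuscitated arrest, no VT over 30 s recorded | Not counted | 6.5.3 |
| Sudden death, no VT over 30 s recorded | Not counted | 6.5.3; all-cause mortality in MACE |

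The gap is rows three to six. Polymorphic VT over 30 seconds is not part of it, because the definition sets no limit on morphology.

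A patient who survives VF after the first month is not covered by the MACE components listed in 2.2.2 or by the perioperative SAE endpoint. That patient reaches a table only through 6.5.3, which places arrhythmias under MACE although 2.2.2 does not list them there.

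**Step 2. Size per patient.** The protocol states no event rate, power or precision for this endpoint, so there is no figure to reproduce. With n = 10 per arm (6.3), one patient is 1/10 = 10 percentage points.

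**Step 3. Illustration with assumed event numbers.** Suppose x cell-therapy patients have only events from rows three to six. The current definition reports 0/10; a definition that includes them reports x/10. The exact (Clopper-Pearson) 95% limits are: lower = Beta quantile at 0.025 with parameters x and n − x + 1; upper = Beta quantile at 0.975 with parameters x + 1 and n − x. For x = 0 the upper limit is 1 − 0.025^(1/10) = 30.8%.

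| Assumed x | Current definition | Wider definition |
|---|---|---|
| 1 | 0/10 (0 to 30.8%) | 1/10 = 10% (0.3 to 44.5%) |
| 2 | 0/10 (0 to 30.8%) | 2/10 = 20% (2.5 to 55.6%) |
| 3 | 0/10 (0 to 30.8%) | 3/10 = 30% (6.7 to 65.2%) |

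**Step 4. Chance that the endpoint shows anything.** Let p be the true risk of malignant ventricular arrhythmia per patient and f the share of affected patients who do not meet the 30-second wording (both assumed). The chance of at least one primary event in 10 patients is 1 − [1 − p(1 − f)]^10.

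| p | f = 0 | f = 25% | f = 50% | f = 75% |
|---|---|---|---|---|
| 10% | 65% | 54% | 40% | 22% |
| 20% | 89% | 80% | 65% | 40% |

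For example, p = 20% and f = 50% give 1 − 0.9^10 = 65%, against 1 − 0.8^10 = 89% when every type counts.

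**The case against.** The strongest reply is that nothing is lost to the trial. Section 6.5.3 counts arrhythmias and SAEs by event and by subject, and deaths are a MACE component. The trial is exploratory, no success threshold or stopping rule hangs on this endpoint, and 0/10 with sustained VT would be a true statement of a clearly named endpoint. This stands as a limit on the harm: the events are outside the primary line, not hidden. It does not remove the mismatch between the primary definition and the risk stated in Section 8.4.

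The example of early termination is also less likely here than in patients with devices. A previous ICD or CRT is an exclusion, so termination within 30 seconds would need external defibrillation or a device implanted later. That is fair, but it leaves VF and unrecorded sudden death untouched.

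A wider definition would not make the arms statistically distinguishable either. Even 3/10 against 0/10 gives a Fisher's exact p of 0.21. The gain is in what the descriptive result reports.

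A reader might go further and infer that patients who die are counted as free of VT, or that the worst outcomes improve the safety rate. The protocol does not support either inference. Section 6.5.1 states no denominator rule, and a statistical analysis plan may settle how deaths are handled. An uncounted VF leaves the numerator where it was; it does not lower the rate.

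**Conclusion.** The point holds as a gap in the event definition. Followed as written, the primary arrhythmia result can read 0/10 while patients in that arm have had VF, VT terminated early for haemodynamic compromise, or an arrest or sudden death without recorded VT over 30 seconds. Each such patient is 10 percentage points in an arm of 10. The difference is 10 to 30 points under the assumed 1 to 3 events. Those event numbers, and the risks in Step 4, are illustrations and not predictions. The classification itself rests only on the wording of the synopsis and Sections 2.2.1, 2.2.2, 6.5.1 and 6.5.3.

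**What to change.** In the synopsis and Section 2.2.1 together, define the primary arrhythmia event as the first of:
- VT lasting more than 30 seconds;
- VT of any length that requires termination for haemodynamic compromise;
- VF;
- resuscitated cardiac arrest;
- sudden death presumed arrhythmic, with a stated definition.

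Report VT over 30 seconds as a component, so that the present endpoint stays visible. Rename the endpoint to match, and carry the new name into Section 6.5.1.

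The cost is mainly wording and case report form fields. No treatment, visit or procedure changes, because these events already fall under adverse event and SAE reporting. Two costs are real. The reported rate may be higher, and the existing investigators must attribute the cause of sudden deaths. Because the trial is open-label and Section 6.4 blinds only the assessors of efficacy, the definition used for that attribution should be written down before any death is classified.

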2.2.2 Secondary endpoints

Efficacy:

- 1. Cardiac MRI Assessment of Left Ventricular Function:
 - o Comparative analysis of baseline versus postoperative measurements at 6, and 12 months, including: Infarcted size; End-diastolic lateral wall thickness; Focal septal thickness; Ejection fraction; End-diastolic volume; End-systolic volume; Stroke volume; Cardiac output; Myocardial density; End-diastolic myocardial mass
- 2. Echocardiographic Evaluation of Left Ventricular Function:
 - o Comparative analysis of baseline versus postoperative measurements at 6, and 12 months, including: End-diastolic septal thickness; Left ventricular end-diastolic

diameter; Left ventricular end-systolic diameter; Left ventricular posterior wall thickness at end-diastole; Left atrial diameter; Left ventricular ejection fraction; Mitral inflow velocity profile (E/A ratio)

- 3. Myocardial Perfusion Imaging (PET/ECT):
 - o Comparative analysis of left ventricular perfusion at preoperative, 6-month, and 12-month postoperatively
- 4. Six-Minute Walk Test (baseline, 6 and 12 months)
- 5. NYHA Functional Classification (baseline, 6 and 12 months)
- 6. Minnesota Living with Heart Failure Questionnaire (MLHFQ) (baseline, 6 and 12 months)
- 7. Incidence of Major Adverse Cardiac Events (MACE) including: Mortality; Non-fatal myocardial infarction; Heart failure rehospitalization

Safety:

- 1. Incidence of Perioperative Serious Adverse Events (SAE) Incidence: Mortality; Nonfatal myocardial infarction; stroke; cardiac perforation; cardiac temponade, etc.
- 2. Alloimmune Response Monitoring (PRA, DSA): (baseline, 1, 6 and 12 months)
- 3. Perioperative Electrocardiographic Monitoring (Within 1 month postoperatively)
- 4. Laboratory Tests, including Complete blood count, Comprehensive metabolic panel; NT-proBNP;Troponin; Myocardial enzyme profile; Procalcitonin; Immunological panel (C3, C4, IgA, IgG, IgM); Coagulation profile, etc.

3 STUDY DESIGN

This is a single-center, open-label, randomized controlled trial involving 20 eligible subjects who meet the inclusion/exclusion criteria. Subjects will be randomly allocated in a 1:1 ratio into two groups:

- Control Group: Standard CABG treatment only
- Cell Therapy Group: CABG + cellular transplantation (dose: 2 × 10⁸ cells) + perioperative immunosuppressive therapy

Postoperative Management:

All patients will undergo rigorous perioperative monitoring (within the first postoperative month) with comprehensive contingency protocols in place.

Follow-Up & Assessments:

Both groups will undergo identical follow-up evaluations at 1, 6, and 12 months, including:

Protocol (version 6.1)

Version data: 2021.08.01

Confidential
Page 17 of 38

Imaging studies (as per protocol), Laboratory investigations, Functional assessments. Documentation will be maintained via case report forms (CRFs) to ensure accurate and reliable data acquisition.

3.1 Inclusion Criteria

Subjects are eligible to be included in the study only if all of the following criteria apply:

- 1. Aged 35-75 (including 35 and 75).
- 2. Have signed the Informed Consent Form.
- 3. Patients have chronic left ventricular dysfunction.
- 4. Patients have NYHA Class III-IV cardiac function in spite of optimal heart failure maximally tolerated guideline-directed medical therapy.
- 5. Patients have indications for Coronary Artery Bypass Grafting.
- 6. 20% ≤ LVEF ≤ 45% as determined by echocardiogram (data collected up to 6 months prior to inclusion evaluation are valid; data collected within 1 month since a myocardial infarction are invalid).
- 7. Weakening or absence of segmental regional wall motion as determined by standard imaging.

3.2 Exclusion Criteria

- 1. PRA \geq 20% or DSA-positive.
- 2. Previous implantation of ICD, CRT or similar treatment.
- 3. Valvular heart disease or received heart valvular disease
- 4. Previous percutaneous transluminal coronary intervention (PCI)
- 5. Atrial fibrillation
- 6. History of sustained ventricular tachycardia or sudden cardiac death.
- 7. Baseline glomerular filtration rate <30ml/min/1.73m2.
- 8. Liver dysfunction, as evidenced by enzymes (AST and ALT) greater than three times the ULN.
- 9. Hematological abnormality: A hematocrit <25% as determined by HCT, white blood cell<2500/ul or platelet values <100000/ul without another explanation.
- 10. Known, serious radiographic contrast allergy, penicillin allergy, streptomycin allergy.

Protocol (version 6.1)

Version data: 2021.08.01

Confidential
Page 18 of 38

- 11. Coagulopathy (INR>1.3) not due to a reversible cause.
- 12. Contra-indication to performance of an MRI scan.
- 13. History of organ transplant.
- 14. Clinical history of malignancy within 5 years (patients with prior malignancy must be disease-free for 5 years).
- 15. Non-cardiac condition that limits lifespan <1 year.
- 16. Chronic therapy with immunosuppressant medication, such as glucocorticoids and TNF α antagonist.
- 17. Patients' allergy to or contra-indication to immunosuppressants.
- 18. Serum positivity for HIV, HBV, HCV, TP.
- 19. Currently enrolled in other investigational therapeutic or device study.
- 20. Female patient who is pregnant or breast-feeding.
- 21. Other conditions that researchers consider not suitable to participate in this study.

4 STUDY TREATMENT

4.1 Treatment and dosage

4.1.1 Treamtment

All enrolled subjects will undergo standardized coronary artery bypass grafting (CABG) in accordance with established clinical guidelines. For patients in the cell therapy group, the treatment protocol incorporates myocardial cell transplantation alongside the standard CABG procedure. Following completion of graft anastomoses, a total of 2×10^8 allogeneic human regenerative cardiomyocytes are administered via epicardial injection at 10 sites surrounding the infarcted myocardial region.

Patients in the Cell therapy group were administered the following immunosuppressive regimen: intravenous immunoglobulin (2.5 g, IV) on preoperative day 1, intraoperative day (IOD), and postoperative day (POD) 3, combined with methylprednisolone (500 mg, IV) on preoperative day 1; rituximab (20 mg, IV) on IOD and POD4 to target CD20+ B-cell depletion; oral tacrolimus started preoperative day 3 and dose-adjusted to maintain trough levels within the target range of 3-5 ng/mL, as monitored by blood drug concentration until POD28, concurrently with mycophenolate mofetil (1 g, orally on preoperative day 1, increasing to 1.5 g/day until POD28) and prednisone (20 mg/day started IOD until POD28). The Control group did not receive any immunosuppressive medications. All study subjects

Protocol (version 6.1)

Version data: 2021.08.01

Confidential
Page 19 of 38

undergo intensive postoperative monitoring in the ICU with comprehensive emergency protocols implemented as needed.

4.1.2 Dosage form and dosage

Cell Type: Allogeneic human regenerative cardiomyocytes

[figure not shown]
Dosage: A total of 2×10^8 cells are administered via intramyocardial injection, divided equally across 10 sites (250–500 µL per injection).

Administration: The procedure is performed intraoperatively following completion of graft anastomoses during CABG.

Control Group receive standardized CABG alone.

5 STUDY PROCESS

5.1 Study Flowchart

5.2 VISIT AND ASSESSMENT SCHEDULE

All data collection procedures for this study are detailed in Table 3

Protocol (version 6.1)

Version data: 2021.08.01

Confidential
Page 20 of 38

Table 3 Visit and Assessment Schedule

	Baseline		Treatm	ent period		Follow-up			
Day (D) Month (M)	D-14 to D-1	D0	D1-D7	D14	D21	M1±7d	M6±14d	M12±14d	
Informed Consent	X								
Medical History and Physical Examination	X					X	X	X	
Vital Signs	X	X	X	X	X	X	X	X	
12-Lead ECG	X		X	X	X	X	X	X	
Concomitant Medications	X	X	X	X	X	X	X	X	
Coronary Angiogram	X								
(SYNTAX score)									
Cell transplantation documentation		X							
Echocardiography	X						X	X	
Cardiac MRI	X						X	X	
PET/ECT	X						X	X	
CT Scan (Chest/abdomen/pelvis)	X						X	X	
6 Minute Walk Test	X						X	X	
NYHA classification	X						X	X	
MLHFQ Score	X						X	X	
Holter Monitoring	X		X	X	X	X	X	X	
(24-hour ECG)									
Cardiac enzymes, troponin	X		X	X	X	X	X	X	
NTproBNP	X		X	X	X	X	X	X	
Complete Blood Count, Procalcitonin	X								
Blood type	X								
Biochemistry	X		X	X	X	X	X	X	
Urinalysis, Fecal Analysis	X					X	X	X	
Thyroid function tests (TSH, FT3, FT4)	X					X	X	X	
Tumor markers	X						X	X	
Immunogenicity	X			X		X	X	X	
Viral Serology	X			X	X	X	X	X	
Coagulation	X		X	X	X				
HLA Typing	X								
PRA	X					X	X	X	
DSA	X					X	X	X	
Cytokine Panel	X		X	X					

Protocol (version 6.1)
Version data: 2021.08.01

Confidential
Page 21 of 38

	Baseline	Treatment period				Follow-up		
Day (D) Month (M)	D-14 to D-1	D0	D1-D7	D14	D21	M1±7d	M6±14d	M12±14d
Adverse Events		X	X	X	X	X	X	X

Confidential Page 22 of 38

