	 Incidence of perioperative serious adverse events (SAEs): Such as Mortality, Non-fatal myocardial infarction, Stroke, Cardiac perforation, Cardiac tamponade, etc. Allogeneic immune monitoring: PRA, DSA (2 week, 1, 3, 6 and 12 Month Post-operation) 					
	3. Perioperative cardiac monitoring: (1 Month Post-operation)					
	Efficacy:					
	Left ventricular function assessment:					
	2. Six-minute walk test: o Distance walked measured at 6 and 12 months postoperatively.					
	3. NYHA functional classification: • Assessed at 6, and 12 months postoperatively.					
	 4. Quality of life evaluation: Minnesota Living with Heart Failure Questionnaire (MLHFQ) administered at 6, and 12 months postoperatively. 					
	5. Major adverse cardiac events (MACE) incidence: o Mortality; Non-fatal myocardial infarction; Heart failure-related rehospitalization					
Statistical Methods and Data Analyses	The trial results will be analyzed primarily using descriptive statistics.					

	Continuous variables will be presented as mean ± standard deviation, along with median, minimum, and maximum values. 95% confidence intervals for means will be estimated using the t-distribution method. Between-group comparisons of means will be performed using Student's t-test. Categorical and ordinal data will be summarized as frequencies (percentages) and rates. 95% confidence intervals for rates will be calculated using the Miettinen method. Between-group comparisons of proportions will be conducted using Fisher's exact test. Longitudinal comparisons (e.g., PRA, DSA, 6-minute walk distance, NYHA functional class, MLHFQ scores) will be analyzed using repeated measures ANOVA to assess dynamic changes over time.
Duration	2 years

.

LIST OF ABBREVIATIONS

iPSC	Induced pluripotent stem cells
HF	Heart failure
CABG	Coronary artery bypass graft
ICD	Implantable cardioverter defibrillator
LVEF	Left ventricular ejection fraction
LVEDV	Left ventricular end-diastolic volume
LVESV	Left ventricular end-systolic volume
MRI	Magnetic resonance imaging
CT	Computed tomography
cTnI	Cardiac troponin I
cTnT	Cardiac troponin T
CKMB	Creatine phosphokinase-Mb
NT-proBNP	N-terminalpro-brain natriuretic peptide
PCT	Procalcitonin
TSH	Thyroid stimulating hormone
ECG	Electrocardiogram
NYHA	New York Heart Association
MACE	Major adverse cardiac events
MLHFQ	Minnesota Quality of Life Questionnaire for Heart Failure
6MWD	6min walking test distance
PCI	Percutaneous coronary intervention
HLA	Human leukocyte antigen

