Mycophenolate Sodium: This novel immunosuppressive agent employs a sodium salt substitution for the ester moiety present in mycophenolate mofetil, aiming to reduce gastrointestinal adverse effects associated with the ester group while maintaining efficacy in preventing transplant rejection. The most frequently reported adverse drug reactions include leukopenia and diarrhea. Additional potential adverse effects encompass infections; hematological abnormalities; headache; cough; gastrointestinal disturbances; abnormal liver function tests; elevated serum creatinine; and rash.

Basiliximab for Injection (e.g., Simulect): As an interleukin-2 (IL-2) receptor antagonist, basiliximab is associated with adverse reactions primarily including constipation, urinary tract infection, pain, nausea, hypertension, anemia, headache, hyperkalemia, hypercholesterolemia, surgical wound complications, weight gain, elevated serum creatinine, hypophosphatemia, diarrhea, and upper respiratory tract infection.

Safety Monitoring During Immunosuppressive Therapy: Subjects enrolled in this study will receive immunosuppressive therapy for a maximum duration of one month at reduced dosing levels. To mitigate the potential adverse effects associated with these agents, rigorous safety monitoring will be implemented throughout the dosing period. This includes scheduled assessments of hematological parameters, renal and hepatic function, quantitative immunoglobulin levels and lymphocyte subsets, as mandated by the protocol. Vigilant clinical monitoring for signs of adverse events or complications will be maintained. Prophylactic measures, including anti-infective prophylaxis and nutritional support, will be implemented per protocol-specified guidelines.

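### Table 3 schedules blood count and procalcitonin at baseline only, although both are secondary safety endpoints and section 8.3 relies on scheduled haematology during immunosuppression

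*Protocol*

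**What the plan says.** Section 5.2 of the protocol states: "All data collection procedures for this study are detailed in Table 3". In that table the row "Complete Blood Count, Procalcitonin" is marked in the baseline column (D-14 to D-1) and nowhere else.

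Three other sections presuppose later values:

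- Section 2.2.2, secondary safety endpoint 4, begins "Laboratory Tests, including Complete blood count, Comprehensive metabolic panel; NT-proBNP;Troponin; Myocardial enzyme profile; Procalcitonin" and goes on to an immunological panel and a coagulation profile.
- Section 6.5.3 says: "Clinical laboratory parameters, vital signs, and physical examination findings will be summarized according to study visit". It adds: "The analysis will describe the observed values at each visit during the trial as well as the changes relative to baseline values".
- Section 8.3, on monitoring during immunosuppression, says: "This includes scheduled assessments of hematological parameters, renal and hepatic function, quantitative immunoglobulin levels and lymphocyte subsets, as mandated by the protocol".

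On treatment, section 4.1.1 gives the cell therapy arm tacrolimus, mycophenolate mofetil and prednisone to postoperative day (POD) 28, plus rituximab. For the other arm it says: "The Control group did not receive any immunosuppressive medications".

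A separate timing mismatch concerns the antibody tests. The synopsis line reads "PRA, DSA (2 week, 1, 3, 6 and 12 Month Post-operation", whereas section 2.2.2 and Table 3 both give baseline and 1, 6 and 12 months.

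**The concern.** A change from baseline needs a value after baseline, and Table 3 provides none for these two tests. If sites follow it, the by-visit summaries must be built from whatever tests were ordered clinically. In an open-label trial the treating staff know who is immunosuppressed, so the timing and frequency of such tests may differ between arms. A comparison of 10 patients with 10 would then partly reflect who was tested and when.

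For blood count, patient safety is also at stake. Section 8.3 lists haematological abnormalities among the reactions to tacrolimus, and leukopenia among the most frequent reactions to mycophenolate. The mycophenolate text describes the sodium salt, while the regimen in 4.1.1 uses mofetil. Scheduled haematology in the first month is therefore a real safeguard, and section 8.3 presents it as something the protocol already requires.

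**Working it through.** No formula is involved. The check is a count of the marks in Table 3 against the tests named in endpoint 4 of section 2.2.2.

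**Inputs.** Table 3 has eight columns: baseline, D0, D1-D7, D14, D21, M1, M6 and M12. No laboratory row is marked at D0, so at most six post-operative columns carry laboratory draws.

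| Test named in 2.2.2 | Table 3 row | Post-operative marks | Where |
|---|---|---|---|
| Blood count | Blood count, procalcitonin | 0 | none |
| Procalcitonin | Blood count, procalcitonin | 0 | none |
| Metabolic panel | Biochemistry | 6 | D1-D7, D14, D21, M1, M6, M12 |
| NT-proBNP | NT-proBNP | 6 | same six |
| Troponin | Cardiac enzymes, troponin | 6 | same six |
| Myocardial enzymes | Cardiac enzymes, troponin | 6 | same six |
| Coagulation | Coagulation | 3 | D1-D7, D14, D21 |
| Immunological panel | Immunogenicity (assumed match) | 4 | D14, M1, M6, M12 |

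The last match is an assumption, because the protocol does not define the Immunogenicity row.

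**Endpoint coverage.** Of the 8 named tests, 2 have a Table 3 row with no post-operative mark: blood count and procalcitonin.

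**Coverage during dosing.** The columns wholly within dosing to POD28 are D1-D7, D14 and D21, so 3 columns. Blood count is marked in 0 of them. M1±7d, taking M1 as day 30, spans days 30 − 7 = 23 to 30 + 7 = 37. It can fall on either side of POD28 and is not counted.

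**Is the gap filled elsewhere?** The synopsis says laboratory results are recorded at each visit, and section 3 lists laboratory investigations at follow-up. Neither names a test. Section 8.3 refers to haematology as scheduled but gives no days. No other section schedules a blood count or procalcitonin after baseline.

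**After correction.** Marking the row as biochemistry is marked raises it from 1 of 8 columns to 7 of 8, with 6 post-operative columns, 3 of them wholly within dosing.

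**PRA and DSA.** The synopsis line has 5 post-operative times (2 weeks and 1, 3, 6 and 12 months). Section 2.2.2 and Table 3 have 3 (1, 6 and 12 months). Table 3 has no 3-month column, and the synopsis itself plans follow-up visits at 1, 6 and 12 months only.

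**The case against.** The strongest reply is that Table 3 is not exhaustive in practice, whatever section 5.2 says. Tacrolimus trough levels (4.1.1), lymphocyte subsets (8.3), and continuous ECG and remote rhythm monitoring (8.4) are all required and have no row. On that reading section 8.3 itself orders haematology and only the days are missing. All patients also go to intensive care, where blood counts are routine, and section 3 promises both arms identical follow-up evaluations at 1, 6 and 12 months. This makes it unlikely that counts would stop at baseline, and it means that uneven testing between arms is a possibility, most plausible in the first month, rather than a certainty. It does not close the gap: those sections give no day for a post-operative blood count, and routine care does not secure study values at D14, D21 or the follow-up visits.

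The conflict with section 6.5.3 can be narrowed. It is a general reporting rule and does not require every test at every visit; coagulation, for example, stops at D21. What remains is that with no post-baseline value there is no change from baseline to report.

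Procalcitonin is the weaker half. Section 8.3 does not mention it, so its case rests on 2.2.2 and 6.5.3, and values at M6 and M12 are the least necessary. Endpoint 4 also carries no time points of its own and is absent from the synopsis endpoint list.

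The table could have been damaged in conversion from PDF, but that is unlikely. The row keeps its empty cells just as the genuinely baseline-only rows do (blood type, HLA typing), and neighbouring rows keep all their marks. A look at the original is still sensible.

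**Conclusion.** The concern holds: the schedule is wrong as written. Blood count and procalcitonin have 0 of 6 possible post-operative laboratory columns although both are named safety endpoints, and blood count has 0 of the 3 columns inside the dosing period although section 8.3 depends on scheduled haematology there. The case is strongest for blood count during immunosuppression and weaker for late procalcitonin. The primary endpoints are not affected. The most likely cause is marks left out of one row, but a site following the table would not collect the data. The conclusion assumes that the table is reproduced faithfully. The PRA and DSA mismatch is separate and minor.

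**What to change.** Mark the blood count and procalcitonin row at D1-D7, D14, D21, M1, M6 and M12 in both arms, using the biochemistry draws already scheduled. If the sponsor wants to economise, procalcitonin at M6 and M12 is the part to drop, with 2.2.2 then stating its time points.

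For PRA and DSA, keep one list. Either correct the synopsis line to baseline and 1, 6 and 12 months, or add both tests at the existing D14 visit in 2.2.2 and Table 3 and delete the 3-month time unless a 3-month visit is created.

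**Cost.** One table row and one synopsis line. Blood count and procalcitonin need no new visit or extra draw. The added assays are 6 × 20 = 120 of each test if D1-D7 counts as one draw. If it means seven daily draws, the figure is (7 + 5) × 20 = 240 of each. A 3-month PRA and DSA sample, if wanted, would need a new visit in both arms.
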